Nearly all of the studies involving EIAH mechanisms and athletes have used either running or cycling as the mode of exercise. However, competitive swimming is an interesting, yet understudied, athletic arena in which to examine EIAH. There is limited evidence (Holmer et al., 1974; Labreche, 2012; Spanoudaki et al., 2004) to suggest that competitive swimmers might experience EIAH. However, it is difficult to draw definitive conclusions from these studies, as they likely either did not have an adequate subject population (Holmer et al., 1974) or did not utilize an exercise protocol with sufficient intensity or duration (Labreche, 2012; Spanoudaki et al., 2004) in which to determine the presence of EIAH. There are numerous plausible mechanisms by which EIAH could develop in swimmers, especially those that are highly-trained. First, swimming occurs 1) in water, with 2) a horizontal body position, and both of these conditions cause an increase in venous return of blood to the heart which would theoretically increase pulmonary capillary pressure (Pendergast et al., 2015). Second, swimmers breathe at incredibly high flow rates (Leahy et al., 2019) with their lungs almost completely inflated (Li, 2016), both of which serve to increase pulmonary capillary pressure (Fu et al., 1992). Third, breathing in competitive swimming is "phase-locked," meaning swimmers can only breathe when their face is out of the water "in-phase" with their swimming stroke, and this ultimately leads to a relative hypoventilation compared to land exercise (Li, 2016). Finally, there is myriad literature linking swimming and pulmonary edema, and this phenomenon is well-chronicled in swimmers of many ages and abilities (Adir et al., 2004; Hohmann et al., 2018).

Therefore, the goals of the present study are twofold:

- 1. To examine whether EIAH occurs in highly-trained swimmers, and
- 2. To examine histamine release as a mechanism by which EIAH occurs in highly-trained athletes.

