#### **Objective(s)**

### 2.1 **Primary Objective**

Aim 1. To confirm whether that highly-trained swimmers experience EIAH

It is hypothesized that highly-trained swimmers will experience EIAH, as evidenced by a decrement in peripheral capillary oxyhemoglobin saturation  $(S_pO_2)$  of 5% or greater from rest to submaximal and/or maximal exercise.

Aim 2. To test whether a pharmacological agent that is a competitive inhibitor to histamine (cetirizine HCI) can improve nadir  $S_pO_2$  during submaximal (70 and/or 85%  $\dot{V}O_{2max}$ ) and/or maximal (100%  $\dot{V}O_{2max}$ ) exercise.

It is hypothesized that the pharmacological agents will significantly (p < 0.05) increase nadir SpO2 during all exercise intensities. This will be assessed using a linear mixed model including random effects for subject, subject within-treatment, and subject within-intensity to account for the repeated measures design. Treatments (placebo and cetirizine HCI), intensity (70, 85, and 100% of  $\dot{V}O_{2max}$ ), and the interaction between treatment and intensity will be included. Main effects and interactions will be tested using *F*-tests from a two-way ANOVA.

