- Peripheral capillary oxyhemoglobin saturation (SPO2): This measurement will take place during the experimental trials in the swimming flume in the IU Human Performance Laboratory. A pulse oximetry sensor (Covidien/Medtronic, Dublin, Ireland) will be placed on the subject's forehead after application of a topical vasodilator (Finalgon; Boehringer Ingelheim, Ingelheim am Rhein, Germany). Though the probe has its own adhesive, an adhesive bandage patch (Tegaderm; 3M, Saint Paul, MN) will be placed over the top to further secure and waterproof the probe below a standard swimming cap. SPO2 will be monitored through a standard bedside pulse oximetry unit (Nellcor N600x; Covidien/Medtronic, Dublin, Ireland) outputting an analog signal to a customized A/D board (Hector Engineering, Ellettsville, IN) and recorded at a 1 Hz sampling frequency by a customized computer program (DasyLab 13.0; Measurement Computing Corporation, Norton, MA).
- Indirect calorimetry: During the experimental trials in the swimming flume, resting and exercise metabolic (VO2 and VCO2) and ventilatory (VE, fB, and VT) variables will be

measured breath-by-breath using a portable metabolic computer (K5; Cosmed, Rome, Italy) suspended above the Endless Pool and adapted for swimming exercise (Aquatrainer, Cosmed, Rome, Italy). This portable system has been determined to be valid and reliable while using breath-by-breath mode (Guidetti et al., 2018) and will be calibrated according to the manufacturer's instructions prior to each test. The swimmer will breathe through a customized two-way, nonrebreathing snorkel mouthpiece (Hans Rudolph, Shawnee, KS).

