- Graded exercise test: After a self-determined warm-up and a rest period of at least 2 minutes, a progressive maximal exercise test will be performed in a specially constructed, customized variable water flow pool (Endless Pools, Aston, PA, USA), with subjects swimming against a flow rate of approximately 1.5 m·s for men and 1.31 m·s for women tethered to a pulley with a 1.2 and 1 kg mass, respectively. After two minutes, the tethered mass will be increased by 0.2 kg every two minutes until each subject reaches volitional exhaustion. Metabolic and ventilatory variables and SPO2 will be measured as described below. Subjects' heart rates during the tests will be continuously recorded (Cardio Swim HR Monitor; Freelap, Switzerland). VO2MAX will be considered as the maximal value attained during the test, provided at least two of three criteria are met, which will include an RER of greater than 1.05, achievement of 90% of age-predicted maximal heart rate, and an increase in VO2 of less than 0.15 L/min over the previous workload. Plasma histamine, whole blood histamine, and histamine release will be measured before and after this test as previous.
- Constant load tests: Following the maximum exercise test, subjects will perform constant load swimming exercise at approximately 70 and 85% of subjects' previously recorded HRMAX during that session. The tethered mass used to elicit the workloads will be estimated during the first 20-minute rest period by performing a linear regression between HR and tethered mass to approximate the tethered mass that would elicit 70 and 85% of maximum HR. Subjects will swim for 5 minutes. Metabolic and ventilatory variables and SPO2 will be measured as described below. Plasma histamine, whole blood histamine, and histamine release will be measured following these tests as previous.
- Drug administration An opaque sugar-free gelatin capsule (Capsuline, Dania Beach, Florida, USA) will be administered 60 minutes prior to testing and will either be empty (placebo) or contain CH (10 mg; Zyrtec®; Johnson & Johnson, New Brunswick, NJ, USA) according to the visit condition.

Timeline of procedures:

Screening Visit (Visit 1): Once participants arrive at the laboratory, an investigator will
obtain written informed consent after all procedures and study risks are fully explained

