- Experimental Trials (visits 3 and 4): Prior to all testing sessions, participants will be asked to abstain from allergy medication for 48 hours, intense exercise for 24 hours, caffeine and alcohol for 12 hours, and food for 2 hours. Prior to the sessions 3-4, participants will also be asked to consume a similar diet the night before and day of each testing session. Women participants will be asked to self-identify when their last menses occurred. In order to prevent sex differences caused by fluctuations in hormone across the menstrual cycle, women participants will only be tested during the first 7 days following menstruation (when estrogen and progesterone hormones are at their lowest levels) for sessions 2-4 (Allen et al., 2016). Apart from receiving a placebo (PL) or drug treatment (CH) prior to exercise, participants will perform identical protocols on each visit to the laboratory. Participants will report to the lab and consume either a placebo or CH pill, followed by a health history update questionnaire and their resting pulmonary function will be measured. Participants will then complete a self-selected warm-up that will be standardized across the two testing sessions, followed by instrumentation. The exercise protocol beings with a progressive swimming test to maximum aerobic capacity (VO2max) in a swimming flume, followed by two constant load work bouts at approximately 70 and 85% of the previously recorded HRmax while peripheral capillary oxyhemoglobin saturation ( $S_pO_2$ ) is continuously monitored. Participants will receive a 20-min break between each work bout. Drug treatments will be assigned in a double-blind, randomized crossover fashion such that each participant receives each treatment. Concentrations of plasma histamine, whole blood histamine, and histamine release will be assessed from a venous blood draw one hour prior to commencement of the aerobic capacity test, and immediately following the aerobic capacity test and each of the two constant load bouts.

**8.0 Study Calendar** The following procedures will be undertaken during the visits.

Table 1: Description of Stud	v Procedures that will take	place on each visit to the laboratory.
	y i roccuures that will take	

STUDY PROCEDURES	Screening (Visit 1)	Selection Exercise Test (Visit 2)	Experimental Trials – Randomized Crossover (Visits 3-4)	
			Placebo	Cetirizine HCI
Height	Х		Х	Х
Weight	Х		Х	Х
Heart rate	Х		Х	Х
Urine specific gravity		Х	Х	Х

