Insufficient data exist to establish a prevalence rate of EIAH among endurance athletes. Attempts have been made to establish prevalence rates in cyclists (Powers et al., 1988) and runners (Constantini et al., 2017), however no such data exist for swimmers. Estimates of prevalence rates range from approximately 70% (Constantini et al., 2017) in highly-trained endurance runners to 32% (Coneys et al., 2011) in untrained individuals. As prevalence rates of EIAH have been demonstrated to increase with aerobic training status (Dominelli and Sheel, 2019), it is likely that the true prevalence of EIAH in highly-trained swimmers is between these values. Therefore, to ensure enrollment of an adequate number of swimmers who experience EIAH, a prevalence estimate of 50% will be utilized. Using a binomial distribution and a target of 8 EIAH-afflicted highly-trained swimmers, recruiting 26 swimmers (n = 13 men, n = 13 women) for the Selection Exercise Protocol provides a >95% probability that the population will contain at least 8 EIAH-afflicted highly-trained swimmers. In order to account for potential participant withdrawal, we anticipate recruiting no more than 30 individuals.

Prior to conducting statistical analysis all data will be visually inspected for normality and potential outliers using kernel density and quantile-quantile plots. Summary statistics of the mean, standard deviation, median, and range will be calculated for all variables of interest.

*Hypothesis 1*. EIAH has been previously defined by a decrement in  $S_pO_2$  of  $\ge 5\%$ . Should a participant experience this during submaximal or maximal exercise, the hypothesis will be confirmed.

*Hypothesis 2.* Prior to analyses, any carry-over effect will be identified using a two-way linear mixed model (visit order x time), independent of the drug treatment (placebo, or cetirizine HCI). If a carry-over effect is observed, a regressor for visit order group will be included in all subsequent analyses.

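### Hypothesis 1 counts as confirmed on one swimmer's SpO2 fall, which cannot support a statement about highly-trained swimmers as a group; the qualifying visit and the measurement definitions are also open

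*Combined protocol and SAP*

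**What the plan says.** **The question and the rule.** Section 1.0 gives the first goal as "To examine whether EIAH occurs in highly-trained swimmers". Section 2.1, Aim 1, turns this into a hypothesis: "It is hypothesized that highly-trained swimmers will experience EIAH, as evidenced by a decrement in peripheral capillary oxyhemoglobin saturation", by at least 5% from rest to submaximal or maximal exercise. Section 12.0, Hypothesis 1, repeats the 5% definition and adds: "Should a participant experience this during submaximal or maximal exercise, the hypothesis will be confirmed". That is the whole analysis of Hypothesis 1. There is no count, proportion, interval or reference value. Section 12.0 does plan a mean, SD, median and range for the variables of interest.

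**The measurement.** For SpO2, section 7.0 says: "This measurement will take place during the experimental trials in the swimming flume in the IU Human Performance Laboratory". Table 1 in section 8.0 agrees, so SpO2 exists only for Visits 3 and 4. Each swimmer takes placebo at one of these visits and cetirizine at the other, and nothing else is meant to differ: apart from placebo or "drug treatment (CH) prior to exercise, participants will perform identical protocols on each visit to the laboratory". Aim 2 in section 2.1 expects an effect of the drug: "It is hypothesized that the pharmacological agents will significantly (p < 0.05) increase nadir S p O 2 during all exercise intensities". The SpO2 signal is "recorded at a 1 Hz sampling frequency by a customized computer program". For the constant-load bouts the text reads: "Subjects will swim for 5 minutes. Metabolic and ventilatory variables and S P O 2 will be measured as described below". No description follows; the method stands earlier in section 7.0 and gives a sampling rate but no averaging window.

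**The swimmers.** Section 12.0 selects swimmers for the experimental trials on a large change in histamine release during the selection exercise, and adds four controls with the smallest change. Hypothesis 3 gives the two cohorts pooled as 12.

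**The concern.** The rule and the hypothesis are statements of different kinds. The rule is met by one person; the hypothesis in section 2.1 speaks of highly-trained swimmers. Followed literally, the report would call a primary hypothesis confirmed whether one swimmer desaturated or most of them did.

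The event that triggers the rule is also not fully defined. The rule names no visit, so a fall under cetirizine counts, although cetirizine is the treatment whose effect on SpO2 is tested in Aim 2. Rest is the reference, but not when or over how long it is measured. A nadir is named for Aim 2, but not how it is taken from a one-second trace. These gaps reach further than Aim 1: Aim 2 needs the nadir, and Aim 3 needs resting SpO2 and SpO2 at 100%. If the definitions are chosen after the data are seen, the analyst has discretion over a primary conclusion.

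**Working it through.** **Inputs.** Pooled swimmers n = 12 (section 12.0, Hypothesis 3; also section 5.0 and appendix 17.1). Controls 4 (section 12.0), leaving 12 − 4 = 8 chosen for high histamine release. Three bouts per visit and two visits (section 7.0). EIAH rates discussed in section 12.0: 32%, 50% and about 70%.

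**1. The plan's own figure.** No operating characteristic is given for the Hypothesis 1 rule. The nearest figure is the probability above 95% that 26 swimmers include at least 8 with EIAH at 50% prevalence. The exact binomial gives P(X ≥ 8 | 26, 0.5) = 0.9855, so it reproduces. It concerns recruitment, not the rule.

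**2. What the rule can tell apart.** The exact (Clopper-Pearson) 95% limits for k of n are the 0.025 quantile of Beta(k, n − k + 1) and the 0.975 quantile of Beta(k + 1, n − k).

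| Result | Exact 95% CI | Conclusion under the rule |
|---|---|---|
| 1 of 12 | 0.2% to 38.5% | confirmed |
| 8 of 12 (illustration) | 34.9% to 90.1% | confirmed |

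Check of the first lower limit: 1 − 0.975^(1/12) = 0.002. The intervals treat the 12 as a simple sample, which they are not. They show how different two results with the same stated conclusion can be, and do not estimate prevalence.

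**3. How easily the rule is met.** If swimmers were independent draws with true rate p (an illustration, since they are selected), P(at least one of 12) = 1 − (1 − p)^12:

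- p = 5%: 46.0%
- p = 10%: 71.8%
- p = 32%: 99.0%
- p = 50%: 99.98%

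At the rates the plan itself discusses, the conclusion is close to settled before any data are collected.

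**4. Which visit counts.** With no visit named, each swimmer has 3 × 2 = 6 bouts in which to qualify, against 3 on placebo alone. Counting either visit can leave the number of qualifying swimmers unchanged or raise it, but never lower it.

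**5. The 5% unit.** For resting saturation R (in %), a relative fall of 5% is 0.05 × R points. It differs from a 5-point fall by 5 − 0.05R = 0.05 × (100 − R) points. Assuming R between 95% and 100% (the documents give no resting value), the difference is 0 to 0.25 points. It matters only for borderline swimmers, but under this rule one borderline swimmer can decide the aim.

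**6. What cohort reporting would look like.** 0 of 4 controls: upper limit 1 − 0.025^(1/4) = 0.602, so 0% to 60.2%. 4 of 8 high-release swimmers: 15.7% to 84.3%.

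**The case against.** The strongest reply is that Aim 1 is an existence question. Section 1.0 asks whether EIAH occurs in these swimmers, section 12.0 notes that no swimmer prevalence data exist, and one verified case answers that question. The plural in section 2.1 is unquantified, and the section 12.0 sentence could be meant as a per-swimmer classification. This narrows the point but does not remove it. The rule attaches its conclusion to the hypothesis as worded in section 2.1, nothing says what verifies a case, and a per-swimmer reading leaves the plan with no group-level conclusion.

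Second, the bad case is unlikely on the plan's own rates. Exactly 1 of 12 has probability 12 × 0.5^12 = 0.3% at 50%, and 12 × 0.32 × 0.68^11 = 5.5% at 32%, even before selection for high release. The planned summary statistics would also show part of the difference. Both remarks limit the practical harm. Neither changes what the plan says it will conclude.

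Third, a genuine fall despite cetirizine still shows that EIAH occurs. That is right for the existence question. It fails once swimmers are counted, because the count then mixes the treated and untreated conditions.

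Fourth, Hypothesis 1 carries no test and no error rate. That is true, and it is why the remedy is a change of wording and not of design.

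**Conclusion.** The point holds. The rule lets one swimmer, in any bout on either visit, confirm a primary hypothesis worded for a group; 1 of 12 and 8 of 12 give the same conclusion. It should be fixed before unblinding. It does not endanger the conduct of the trial or the usefulness of the data. The conclusion rests on reading the section 12.0 sentence as written and on n = 12.

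Four stronger readings are not supported:

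- A reader might infer that no resting reference exists. Rest is named in sections 2.1, 2.2 and 12.0; only its timing and duration are missing.
- A reader might infer that each one-second reading is a separate chance of a false confirmation. The readings are serial samples of one oximeter's output, the documents give no artefact rate, and section 13.0 requires data to be plotted and outliers checked for authenticity. These checks set no minimum duration for a fall, but no false-confirmation rate can be calculated.
- A reader might infer that the four controls come on top of the twelve. Hypothesis 3 pools both cohorts at 12, and section 5.0 and appendix 17.1 also give twelve.
- A reader might take k of 12 as a prevalence. The swimmers come from both extremes of histamine release, so a pooled interval describes no definable population.

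**What to change.** **Section 12.0, Hypothesis 1.**

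- Replace the one-participant sentence with: *EIAH was observed in k of n swimmers on the placebo visit.*
- Report this separately for the high-release and control cohorts, each with an exact 95% CI.
- Give the pooled count of 12 descriptively, without an interval.
- State that swimmers were selected on histamine release, so no figure is a prevalence among highly-trained swimmers.

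No minimum count is proposed, because the documents give no basis for a reference rate.

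**Section 7.0.** Before unblinding, fix one definition each of resting SpO2 (time point and duration), of the averaged nadir (window), and of the 5% unit (points or relative percent). Use the same nadir for Aim 2. Correct the cross-reference that points to a later SpO2 description.

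**Cost.** Wording only, with no new visits, data or participants. Aim 1 becomes descriptive. The cohort intervals will be wide, as shown above. Falls seen only on the cetirizine visit no longer count towards Aim 1, and averaging may smooth out some very brief true falls.

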Those selected for further study will visit the Human Performance Laboratory on two occasions separated by at least 48 hours and no more than 60 days. Apart from receiving a placebo (PL) or drug treatment (cetirizine HCl, CH) prior to exercise, participants will perform identical protocols on each visit to the laboratory. Participants will report to the lab and consume either a placebo or CH pill, followed by a health history update questionnaire and their resting pulmonary function will be measured. Participants will then complete a self-selected warm-up that will be standardized across all testing sessions, followed by instrumentation. The exercise protocol beings with a progressive swimming test to maximum aerobic capacity ( $\dot{V}O_{2max}$ ) in a swimming flume, followed by two constant load work bouts at approximately 70 and 85% of the previously recorded HRmax while peripheral capillary oxyhemoglobin saturation (SpO2) is continuously monitored. Participants will receive a 20-min break between each work bout. Drug treatments will be assigned in a double-blind, randomized crossover fashion such that each participant receives each treatment. Concentrations of plasma histamine, whole blood histamine, and histamine release will be assessed from pre- and post-exercise blood samples.

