#### 6.0 Enrollment/Randomization

We plan to recruit up to 30 participants for this project to ensure that at least 24 participants will complete the first two visits of the study.

Participants will be recruited from the Indiana University varsity swim team and the associated professional training group. Indiana University is home to a NCAA Division I swim team that is perennially among the nation's top-10 for both men and women. Participants will be recruited from this group of over 50 swimmers using a standard email script.

[figure not shown]
Potential participants will be given the basic information about the study and schedule an appointment for screening if they indicate that they would be interested in participating. Participants will be provided a with detailed description of study procedures prior to study enrollment. Participants will be asked to read the consent form at this time and be encouraged to ask any questions. Participants can then: 1) sign the consent form; 2) take it home for further consideration; or 3) decide not to participate. Participants will be screened once written informed consent has been given.

Experimental trials 3 and 4 will be completed in a double-blinded randomized crossover design. The randomization order will be determined using a customized program (Excel; Microsoft Corporation, Redmond, WA, USA). Subjects will be randomized using the randomization list by order of enrollment in the study by a researcher listed on the IRB personnel. This researcher will also be responsible for drug administration but will otherwise not participate in any data collection or analyses.

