In order to test for potential differences in the dependent variables of interest, linear mixed models will be used including random effects for subject, subject within-treatment, and subject within-intensity to account for the repeated measures design. Treatment (PL and CH), intensity (70, 85, and 100% of  $\dot{V}O_{2max}$ ) and the interaction between treatment and intensity will be included. Main effects and interactions will be tested using *F*-tests from a two-way ANOVA. Statistical significance will be assessed using a pre-determined  $\alpha$  level of 0.05. Where significant main effects or interactions are observed, estimated marginal means will be used to test for differences in the drug conditions and adjusted for multiple comparisons using Dunnett's method.

*Hypothesis* 3. The correlation between the change in histamine release ( $\Delta$ %Hpre-%Hpost) and the change in SPO2 at  $\dot{V}O_{2max}$  ( $\Delta$ SPO2rest-SPO2@100%) will be assessed in the pooled experimental and control cohorts (n=12) by a Pearson correlation coefficient using a predetermined  $\alpha$  level of 0.05.

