### **13.0 Statistical Data Management**

Primary data will be collected via direct data capture from measurement instruments and stored electronically on an electronic spreadsheet on a password protected computer. The storage location will be backed up manually every week. Quality assurance steps will be confirmed by plotting the data prior to formal analyses. Outliers will be identified and checked for authenticity in the database and other original data documents. Extraction and cleaning of data that will be used for analysis will be carried out after each block of subjects used in the randomization of visits 3, 4, and 5 have completed all laboratory visits.

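### The Hypothesis 2 crossover model has no visit (period) term, and the visit-order regressor offered as a safeguard cannot change the treatment estimate when data are complete

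*Combined protocol and SAP*

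**What the plan says.** Section 5.0 describes a two-treatment, two-visit design: "Drug treatments will be assigned in a double-blind, randomized crossover fashion such that each participant receives each treatment". The flume visits (Visits 3 and 4) are "two occasions separated by at least 48 hours and no more than 60 days".

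For Aim 2, section 2.1 lists as fixed effects "Treatments (placebo and cetirizine HCI), intensity (70, 85, and 100% of" maximal oxygen uptake, plus the interaction. Section 12.0 repeats this: "Treatment (PL and CH), intensity (70, 85, and 100% of" maximal uptake, with the interaction. The random effects are subject, subject within treatment and subject within intensity. Neither section names visit or period.

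Section 12.0 adds a preliminary step: "any carry-over effect will be identified using a two-way linear mixed model (visit order x time), independent of the drug treatment". The consequence of a positive result is: "If a carry-over effect is observed, a regressor for visit order group will be included in all subsequent analyses". The terms visit order and time are not defined, and no significance level is given for this step.

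On allocation, section 6.0 says: "Subjects will be randomized using the randomization list by order of enrollment in the study". Up to 30 swimmers enrol, but twelve go on to the crossover after Visit 2. Section 13.0 implies blocking, with cleaning "after each block of subjects used in the randomization of visits 3, 4, and 5 have completed all laboratory visits", but gives no block size. The calendar in section 8.0 has no Visit 5.

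**The concern.** A swimmer's second flume session can differ from the first for reasons unrelated to the capsule, such as training state up to 60 days later or familiarity with the equipment. In a crossover of twelve, a visit effect left out of the model goes to one of two places. If the two orders are equally filled, it inflates the error term and costs power. If they are not, part of it is added to the cetirizine effect.

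The plan appears to guard against this with the visit-order regressor. That regressor describes differences between swimmers, whereas the treatment contrast is made within swimmers. It therefore corrects neither a period effect nor carry-over. The pretest that triggers it is also doubtful, because its second factor is not defined. Aim 2 is a primary aim, so the treatment test in this model carries one of the trial's main conclusions.

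**Working it through.** **The plan's own figure.** Section 12.0 gives Cohen's f = 1.22, alpha 0.05, power 0.80 and N = 12 from a fixed-effects ANOVA. Using a noncentral F with λ = f²N and df1 = 1, eight groups (2 × 4, the cited study's layout) give a minimum N of 12, with power 0.878. Six groups (2 × 3, this trial) give a minimum N of 10 (power 0.818), and power 0.937 at N = 12. Taking f as given, twelve reproduces, but the calculation has no crossover or period structure. It therefore supplies no within-subject SD for what follows.

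**Notation.** Let d be a swimmer's cetirizine-minus-placebo difference averaged over intensities, τ the drug effect, π the Visit 4 minus Visit 3 effect, and n1 and n2 the numbers taking placebo first and cetirizine first (n1 + n2 = 12). The mean of d is τ + π in the first group and τ − π in the second. SD is that of d within a sequence, in saturation points. SD, π and τ are assumed.

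**Bias without a visit term.** The estimate averages d over all twelve, so its expectation is τ + π(n1 − n2)/12.

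| Split | Bias | Type I error, no visit term (SD 1.5, π 1.5) | With visit term |
|---|---|---|---|
| 6:6 | 0 | 0.007 | about 0.05 |
| 7:5 | 2/12 = 1/6 of π | 0.015 | about 0.05 |
| 8:4 | 4/12 = 1/3 of π | 0.05 | about 0.05 |
| 9:3 | 6/12 = 1/2 of π | 0.15 | about 0.05 |

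**Effect of the regressor.** Order group does not vary within a swimmer, so it cancels from d. Mixed models with the planned random effects were fitted to 30 simulated complete data sets per setting, with true τ = 1.0:

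- Period effect 1.5 at 8:4: mean estimate 1.49 without the regressor, 1.49 with it, and 0.96 with visit and sequence. The formula gives 1.0 + 1.5/3 = 1.5 for the first two.
- Carry-over 2.0 at 6:6: mean estimate −0.01 in all three models. This agrees with 1.0 − 2.0/2 = 0.
- Largest change from adding the regressor: 0.0.

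With one swimmer's second visit missing in a separate example, the regressor moved the estimate only from 1.445 to 1.429.

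**Power at 6:6, without and with a visit term.**

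| τ | SD | π | Without | With |
|---|---|---|---|---|
| 1.5 | 1.5 | 0.5 | 0.86 | 0.88 |
| 1.5 | 1.5 | 1.0 | 0.77 | 0.88 |
| 1.5 | 1.5 | 1.5 | 0.61 | 0.88 |
| 2.8 | 1.5 | 1.5 | about 1.00 | about 1.00 |
| 2.8 | 3 | 1.5 | 0.76 | 0.83 |

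The value 2.8 is the smallest treatment difference in Table 2 (for example 96.5 − 93.7).

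**The pretest, if time means visit.** Visit 4 minus Visit 3 averages π + τ in one order and π − τ in the other. The interaction contrast is therefore 2τ, which is the drug effect itself. Its standard error at 6:6 is SD·√(1/6 + 1/6). For τ = 1.0 and SD 1.5 the noncentrality is 2/0.866 = 2.31 on 10 df. With no carry-over at all, carry-over is then declared in 55% of trials. The rate is 88% for τ = 1.5 (SD 1.5) and 83% for τ = 2.8 (SD 3).

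**The pretest, if it compares the two order groups.** A carry-over of size c shifts the mean of a swimmer's two visits by c/2. With between-subject SD 1 and within-subject variance 1.5²/2 = 1.125, the SD of that mean is √(1 + 1.125/2) = 1.25. For c = 3 the noncentrality is 1.5/(1.25·√(1/3)) = 2.08, and power is 47%. For c = 1 and between-subject SD 2, power is 7%.

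**Chance of an uneven split.** Under simple randomisation of twelve, the probability of 8:4 or worse is 0.39 and of 9:3 or worse 0.15. If the twelve are drawn from a balanced list of 26, these are 0.24 and 0.05. Effective blocking among the twelve would lower both.

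**The case against.** The strongest reply is that visit order might mean first versus second visit. The regressor would then be a period term and could move the estimate, and the aliasing argument would fail. The word group fits sequence better, however, and even on this reading the term enters only after a positive pretest. The wording would still need changing.

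The second reply concerns consequence, and much of it stands. At 6:6 there is no bias and the test is conservative. Averaged over splits with π and SD both 1.5, type I error is 0.051 under simple randomisation and 0.026 for the list of 26, so there is no overall inflation. Clear inflation needs 9:3 or worse. At drug effects like those in Table 2 the power loss is small or nil. A period effect as large as the SD is an assumption, and the familiar flume, session-specific loads and standardised preparation (section 7.0) all work against it. Section 13.0 also hints at blocking, which might secure balance if it operates among the twelve.

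Third, a false carry-over signal triggers a step that does nothing, so it does not bias the drug estimate. That is right. The harm is a possible misreport of carry-over.

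Finally, a visit term does not cure carry-over either. This also stands: the simulation shows the same error in all three models. Protection against carry-over has to come from the separation of the visits.

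**Conclusion.** The concern holds. That the regressor is inert is algebra for complete data, given that order group means sequence; it depends on no assumed SD. The bias fractions are equally exact, but the size of π is unknown, so the absolute bias is too. The type I error and power figures rest on assumed SDs of 1.5 and 3 and period effects up to 1.5 points.

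The practical harm is conditional: lost power at a balanced split, and bias at an unbalanced one that the documents do not rule out. The plan's stated remedy helps in neither case, and its trigger is either confounded with treatment or a low-powered comparison of about 6 versus 6. This should be fixed before analysis, but it does not undermine the design.

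**What to change.** In section 12.0, and in the matching text of section 2.1, include visit (Visit 3 or Visit 4) and sequence as fixed effects in every Hypothesis 2 model. Delete the pretest-driven choice of model. Because no term in this two-visit design removes carry-over, state the basis on which the minimum separation in section 5.0 is relied on.

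In section 6.0, state that sequence is assigned after the twelve are selected, in balanced blocks of stated size. Stratifying by histamine cohort is optional. Reconcile the reference to Visit 5 in section 13.0 with the calendar.

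The cost is wording and one error degree of freedom (11 to 10 for the treatment contrast). If there is no period effect, power for a 1.5-point effect at SD 1.5 falls from 0.88 to 0.877 at 6:6, 0.868 at 7:5, 0.84 at 8:4 and 0.77 at 9:3. Averaged over simple-randomisation splits, the term roughly breaks even when the period effect is one third of the SD (0.848 without, 0.842 with). It gains at two thirds (0.745 against 0.842). The loss at uneven splits is why balanced allocation should accompany the model change.
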